11 LIST OF ABBREVIATIONS

Term	Definition
AE	adverse event
ACLS	advanced cardiac life support
AI	accumulation index
AI_AUC	AUC Accumulation Index; ratio of AUC(TAU) at steady state to AUC(TAU) after the first dose
AI_Cmax	Cmax Accumulation Index; ratio of Cmax at steady state to Cmax after the first dose
AI_Ctau	Ctau Accumulation Index; ratio of Ctau at steady state to Ctau after the first dose
ALT	alanine aminotransferase
ANC	absolute neutrophil count
ANOVA	analysis of variance
aPTT	activated partial thromboplastin time
AST	aspartate aminotransferase
AT	aminotransaminases
AUC	area under the concentration-time curve
AUC(INF)	area under the concentration-time curve from time zero extrapolated to infinite time
AUC(0-T)	area under the concentration-time curve from time zero to the time of the last quantifiable concentration
AUC(TAU)	area under the concentration-time curve in one dosing interval
A-V	atrioventricular
β-HCG	beta-human chorionic gonadotrophin
BA/BE	bioavailability/bioequivalence
%BE	percent biliary excretion
BID, bid	bis in die, twice daily
BLQ	below limit of quantification
BMI	body mass index
BMS	Bristol-Myers Squibb
BP	blood pressure
BRt	Total amount recovered in bile

Term	Definition
%BRt	Total percent of administered dose recovered in bile
BUN	blood urea nitrogen
C	Celsius
C12	concentration at 12 hours
C24	concentration at 24 hours
Ca ⁺⁺	calcium
Cavg	average concentration
CBC	complete blood count
Cexpected-tau	expected concentration in a dosing interval
CFR	Code of Federal Regulations
CI	confidence interval
Cl ⁻	chloride
CLcr	creatinine clearance
CLD	Dialysate clearance of drug from plasma/serum
CLNR	nonrenal clearance
CLR	renal clearance
CLT	total body clearance
CLT/F (or CLT)	apparent total body clearance
CLT/F/fu or CLT/fu	Apparent clearance of free drug or clearance of free if (if IV)
cm	centimeter
Cmax, CMAX	maximum observed concentration
Cmin, CMIN	trough observed concentration
CNS	Central nervous system
CRC	Clinical Research Center
CRF	Case Report Form, paper or electronic
Ct	Expected concentration at a certain time, usually at the end of an expected future dosing interval (eg, concentration at 24 hours, concentration at 12 hours, etc.)
Ctau	Concentration in a dosing interval (eg, concentration at 24 hours, concentration at 12 hours, etc.)
Ctrough	Trough observed plasma concentration

Term	Definition
CV	coefficient of variation
CYP	cytochrome p-450
D/C	discontinue
dL	deciliter
DRt	Total amount recovered in dialysate
%DRt	Total percent of administered dose recovered in dialysate
DSM IV	Diagnostic and Statistical Manual of Mental Disorders (4 th Edition)
EA	extent of absorption
ECG	electrocardiogram
eCRF	Electronic Case Report Form
EDC	Electronic Data Capture
EEG	electroencephalogram
eg	exempli gratia (for example)
ESR	Expedited Safety Report
F	bioavailability
Fb	fraction of bound drug
FDA	Food and Drug Administration
FI	fluctuation Index ($(C_{max}-C_{tau})/C_{avg}$)
FRt	total amount recovered in feces
%FRt	total percent of administered dose recovered in feces
FSH	follicle stimulating hormone
%FE	percent fecal excretion
fu	fraction of unbound drug
g	gram
GC	gas chromatography
GCP	Good Clinical Practice
G criteria	adjusted R^2 value of terminal elimination phase
GGT	gamma-glutamyl transferase
GFR	glomerular filtration rate
h	hour
HBsAg	hepatitis B surface antigen

Term	Definition
HBV	hepatitis B virus
HCV	hepatitis C virus
HCO ₃ ⁻	bicarbonate
HIV	Human Immunodeficiency Virus
HR	heart rate
HRT	hormone replacement therapy
ICD	International Classification of Diseases
ICH	International Conference on Harmonisation
ie	id est (that is)
IEC	Independent Ethics Committee
IMP	investigational medicinal products
IND	Investigational New Drug Exemption
IRB	Institutional Review Board
IU	International Unit
IV	intravenous
K	slope of the terminal phase of the log concentration-time curve
K ₃ EDTA	potassium ethylenediaminetetraacetic acid
K ⁺	potassium
kg	kilogram
λ _{σz}	terminal disposition rate constant
L	liter
LC	liquid chromatography
LDH	lactate dehydrogenase
ln	natural logarithm
Lz_Start	The time point starting the log-linear elimination phase defining the terminal half life
Lz_End	The time point ending the log-linear elimination phase defining the terminal half life
Lz_N	Number of time points in the log-linear elimination phase defining the terminal half life
mg	milligram

Term	Definition
Mg ⁺⁺	magnesium
MIC	minimum inhibitory concentration
min	minute
mL	milliliter
mmHg	millimeters of mercury
MR	medical research
MR_AUC(0-T)	Ratio of metabolite AUC(0-T) to parent AUC(0-T), corrected for molecular weight
MR_AUC(INF)	Ratio of metabolite AUC(INF) to parent AUC(INF), corrected for molecular weight
MR_AUC(TAU)	Ratio of metabolite AUC(TAU) to parent AUC(TAU), corrected for molecular weight
MR_Cmax	Ratio of metabolite Cmax to parent Cmax, corrected for molecular weight
MR_Ctau	Ratio of metabolite Ctau to parent Ctau, corrected for molecular weight
MRT	mean residence time
MS	mass spectrometry
MTD	maximum tolerated dose
µg	microgram
N	number of subjects or observations
Na ⁺	sodium
N/A	not applicable
ng	nanogram
NIMP	non-investigational medicinal products
NSAID	nonsteroidal anti-inflammatory drug
pAUCe	Extrapolated partial AUC from last quantifiable concentration to infinity
Pb	percent of bound drug
PD	pharmacodynamics
PK	pharmacokinetics
PO	per os (by mouth route of administration)
PT	prothrombin time
PTT	partial thromboplastin time

Term	Definition
Pu	percent of unbound drug
QC	quality control
QD, qd	quaque die, once daily
R ²	coefficient of determination
RBC	red blood cell
SAE	serious adverse event
SD	standard deviation
SOP	Standard Operating Procedures
sp.	species
Subj	subject
t	temperature
T	time
TAO	Trial Access Online, the BMS implementation of an EDC capability
T-HALF	Half life
T-HALF _{eff} _AUC	Effective elimination half life that explains the degree of AUC accumulation observed
T-HALF _{eff} _C _{max}	Effective elimination half life that explains the degree of C _{max} accumulation observed)
TID, tid	ter in die, three times a day
T _{max} , T _{MAX}	time of maximum observed concentration
TR_AUC(0-T)	AUC(0-T) treatment ratio
TR_AUC(INF)	AUC(INF) treatment ratio
TR_C _{max}	C _{max} treatment ratio
UR	urinary recovery
%UR	percent urinary recovery
UR _t	total amount recovered in urine
%UR _t	total percent of administered dose recovered in urine
UV	ultraviolet
V _{ss} /F (or V _{ss})	apparent volume of distribution at steady state
V _z	Volume of distribution of terminal phase (if IV and if multi-exponential decline)
W	washout

Term	Definition
WBC	white blood cell
WHO	World Health Organization
WOCBP	women of childbearing potential
x g	times gravity

APPENDIX 1 ADAPTIVE EARLY DECISION FOR DOSE PANEL ESCALATION

Introduction

A model-based cohort escalation rule is established to help decide on opening the next cohort for newly enrolled subjects when current cohort is filled but not all of its subjects are monitored for 2 whole weeks regarding drug toxicity and tolerability. The decision rule would allow treating subject, once available, at the next cohort without waiting for the completion of every subject's AE evaluation period at the current cohort and at the same time keeping decision risk acceptably low.

Please note that AE would be closely monitored throughout the trial for each subject, and the 2 weeks' AE evaluation period mentioned here is for the purpose of cohort escalation only. During the evaluation period, the numbers of subjects who developed drug-related SAE within the same organ system at grade 3 or higher, called AE of interest are counted and the largest number will be used.

Decision Risk

The decision risk is mathematically defined as the probability of observing enough number of event(s) in the still non-evaluable subjects given data collected from evaluable subjects such that cohort escalation is not allowed. Evaluable subjects are those who are observed an AE of interest or complete the AE evaluation period. To enroll subject into the next cohort, the non-adaptive cohort escalation rule requires, among others, no more than one subject being reported drug-related serious adverse event or serious infection and infestation within the evaluation period. Therefore, if one subject is observed with an AE of interest, the decision risk would be the probability of observing at least one more AE of interest in the non-evaluable subjects; if no AE of interest is reported, the decision risk is thus the probability of observing at least two AEs of interest from the non-evaluable subjects.

Decision Data

To take advantage of the titration design, in which subjects could possibly take a higher dose that is to be used initially in the next cohort, the adaptive decision rule makes use of the following three statistics:

- Titration-Dose Evaluable Subjects (nH): the number of subjects who are titrated and complete the evaluation period (2 weeks) starting from the titration's first dose (on day 43).
- Start-Dose Evaluable Subjects (nL): the number of subjects who develop drug related SAE at grade 3 or higher or complete the evaluation period (2 weeks) from the first dose (on day 1) but haven't completed the 2 weeks evaluation period following the first titration dose (on day 43) if being titrated to a higher dose.
- Count of AE of Interest (k): number of subjects with AE of interests, which could happen any time after the first dose of BMS-986004 till the decision making day. Apparently, $k=0$ or 1. Please note that it doesn't distinguish at which stage, prior to or post titration, that such AE happened.

With sample size of 10 for each cohort, the number of non-evaluable subjects is $10-nH-nL$.

Decision Risk Estimation

Calculation of decision risk is based on the method of Bayesian constrained rate estimate with ascending beta prior. It assumes that the rate of AE of interest increases with doses, however, no specific mathematical form is given governing the relationship between dose and rate. In this way, robustness is achieved by avoiding possible model misspecification. It also assumes that rate depends on the maximum dose subject takes, i.e., titrated subjects are equally likely in developing AE of interest as subjects who take the titrated dose right in the beginning. The prior information is solicited from a phase III study of Abatacept IM101174, in which 12 out of 721 subjects (1.7%) were reported to experience drug related SAEs within short term period (half year treatment). The prior used is Beta(0.01, 0.49), which indicates 2% rate and is equivalent of contributing 0.5 subject at each dose.

Decision risk for $k=1$ is listed below (values are provided only for when the number evaluable subjects, $nH+nL$, is at least 5, and at most 9). Bayesian MCMC simulation is performed to compute the posterior predictive probability under R version 3.1.0 with a random seed of 20140625.

Titration-Dose Evaluable Subjects (nH)	Start-Dose Evaluable Subjects (nL)								
	1	2	3	4	5	6	7	8	9
0					43.2	34.1	25.4	16.6	8.3
1				38.6	30.0	22.7	14.6	7.2	
2			36.0	29.1	21.1	13.9	6.8		
3		34.9	27.4	20.0	13.1	6.5			
4	33.9	25.9	19.3	12.9	6.2				
5	25.7	19.3	12.5	6.0					
6	18.4	11.9	5.9						
7	11.8	5.7							
8	5.7								

When $k=0$, decision risk is close to zero, therefore not provided.

Minimum safety requirement:

Other conditions, as listed below, have to meet to open a new cohort

There must be at least 5 evaluable subjects

The start dose of the new cohort or a higher dose must be shown tolerated in the IM140-002 study if such dose was or will be tested.

Decision Rule

Decision rule is derived by comparing decision risk to a pre-selected threshold value when the current cohort is filled and a newly enrolled subject is available to be allocated to the next cohort. If decision risk is less than the threshold value, the subject will be treated at the next cohort (denoted as E in the following table), otherwise, the subject need to wait for more evidence coming up (denoted as W).

An example of decision rule for k=1 is shown below with decision risk being 15%.

Titration-Dose Evaluable Subjects (nH)	Start-Dose Evaluable Subjects (nL)								
	1	2	3	4	5	6	7	8	9
0	W	W	W	W	W	W	W	W	E
1	W	W	W	W	W	W	E	E	
2	W	W	W	W	W	E	E		
3	W	W	W	W	E	E			
4	W	W	W	E	E				
5	W	W	E	E					
6	W	E	E						
7	E	E							
8	E								

Decision rule for k=0 is same as the Minimum safety requirement for any reasonable small threshold value.

APPENDIX 2 ADAPTIVE DOSE SELECTION

Introduction

Bayesian logistic regression model is used to predict an adaptive dose for a given response rate. Simulations of both logistic regression and Bayesian logistic regression are provided to show their performance in predicting dose for pre-selected response rate. New method of analyzing data obtained from the study with titration design is also included. More detailed discussion will be available in the study's statistical analysis plan (SAP).

Adaptive dose selection is not limited to the Bayesian logistic regression model described in this appendix. Alternative modeling includes, for example, nonlinear or linear mixed effect regression of longitudinal platelet count. Specifically, when PK exposure data are available, model based on PK exposure may be a better choice than that on dose only since there are only a few distinct values of doses.

Adaptive dose selection can be performed as early as when the third cohort is about to enroll subjects. However, it is advised that the predicted dose would be more reliable when more data are available, e.g., when the fourth cohort is about to enroll. For safety reasons, the selected dose to be administered at a higher cohort cannot be larger than what is planned for that cohort.

Bayesian Logistic Model Description

The model is described below:

$$\log\left(\frac{p_i}{1-p_i}\right) = \beta_0 + \beta_1(\log(d_i) - \log(75))$$
$$y_i \sim \text{Binomial}(n_i, p_i)$$
$$\beta = \begin{bmatrix} \beta_0 \\ \beta_1 \end{bmatrix} \sim N(\mu, \Psi)$$

[figure not shown]
where, at each dose level i , d_i is dose in mg, p_i is the expected response rate, n_i is the number of subjects treated at dose d_i , and y_i is the number of responders. Model parameters β are assumed a normal distribution with mean μ and variance ψ . Explaining variable, dose, is in log scale, and is subtracted by an offset of $\log(75)$, where 75 is the minimum dose administered at cohort 1. By subtracting such an offset value, intercept parameter μ alone can be interpreted as the log odd value of the expected response rate for cohort 1, and as such it is easy to set prior distribution parameters (shown below).

Prior of the model parameters is set under the following guidelines:

- Model-predicted response rate at each dose level matches the expected rate.
- A 97.5% quantile of the response rate at the lowest dose is around 0.4.
- A 2.5% quantile of the response rate at the highest dose is around 0.35.
- Extremely small probability for β_2 being negative

It is assumed that the response rate at dose of 75mg, 225mg, 675mg, and 1500mg to be 0.2, 0.4, 0.55 and 0.7 respectively. A linear regression using the above data will give prior mean μ to be (-1.33, 0.72) with rounding error. The second and third bullets of the guidelines would make the stand deviation of β_1 to be 0.45, and β_2 to be 0.2. Prior distributions of β_1 and β_2 are assumed to be independent. A 95% credible interval of response rates under prior and without observation data is shown in Figure 1, where the top curve is the upper 97.5% quantile, the center is the mean, and the bottom is the lower 2.5% quantile. The circles represent the expected response rates at the selected doses. It can be seen that the chosen prior would lead to a mean response rate estimate being very close to the expected or assumed, and at the same time the wide region of 95% credible interval indicates that the prior's weak impact on the posterior estimation of response rate when data are observed.

Figure 1: 95% Credible Interval of Response Rate under Prior Only

Special consideration for titration

Non-responders at each cohort other than the maximum 1500mg cohort would be administered higher dose with the hope of becoming responders. Therefore, two response status data may be observed for those non-responders. Due to relative small sample size of each cohort, making use of status data after the titration dose is believed to increase the accuracy of model-based prediction under some reasonable assumptions. Listed in the below are two assumptions used in the adaptive dose selection:

- If a subject responds to a dose, the subject would respond to higher dose with probability 1.

- If a subject does not respond to a dose after 3 administrations, additional dosing at the same dose would not make a subject change from non-responder to responder.

Based on the above assumptions, a new approach is proposed to combine the subjects at two adjacent cohorts to estimate the response rate at the higher dose which is shared by the two cohorts.

Simulation

Trial simulation is done to show the performance of logistic regression and Bayesian logistic regression with starting dose data only or with titration data included. The Settings of simulation parameters are listed below for convenience:

[figure not shown]
- Doses: 75, 225, 675, 1500
- Rate: 0.2, 0.4, 0.55, 0.7
- Conditional response rate for non-responder after titration: 0.25, 0.25, 0.33
- Response rate used to predict dose: 0.7 (equivalently the fourth cohort)
- Number of simulated trials: 1000

Prediction results from four different methods are compared with each other.

- SLogit: Logistic regression with response status from starting dose only
- SBayLogit: Bayesian logistic regression with response status from starting dose only
- DLogit: Logistic regression with response status from both starting dose and titration dose
- DBayLogit: Bayesian logistic regression with response status from both starting dose and titration dose

Simulation results are shown in Figure 2. It can be seen that Bayesian modeling provides less variant and seemingly closer-to-true-value predictions compared to the usual logistic regression. In addition, variation of the predicted dose is smaller by including titration data when same modeling is used.

Figure 2: Predicted Dose from Different Methods

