If dose escalation is stopped due to any of these findings, additional cohorts may receive the same or lower doses of the investigational compound.

At the time of dose escalation, dose levels of new cohorts may be adjusted to lower doses if the accumulated safety data so dictates.

Adaptive dose selection may be performed to adjust some pre-selected doses, e.g., the third or/and fourth cohort doses, using accumulated efficacy and dose or exposure data. Models based on response rate, such as but not limited to (Bayesian) logistic regression, (Bayesian) EMax, may be utilized to predict a dose satisfying certain efficacy criteria, which might be different from the standard. If there are enough responding subjects with multiple platelet measurements, changes of platelet count may be directly modeled by dose and study day to facilitate dose prediction. The selected dose for a cohort should not exceed the originally planned dose for that cohort, i.e., selected dose for cohort C should not be larger than 675mg and it should be at most 1500 mg for cohort D.

The study design schematic is presented in [Figure 3.1.3-1](#).

Figure 3.1.3-1: Study Design Schematic: Short-term period

*Will not apply to subjects entering LTE

Figure 3.1.3-2: Study Design Schematic: Short-term period

Intra-Subject Dose Escalation

[figure not shown]
[figure not shown]

Figure 3.1.3-3: Study Design Schematic: Long term extension period

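### Appendix 2 says the dose-selection prior has little influence; at its earliest permitted use it carries roughly half the weight or more, and the one visible simulation cannot test it

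*Protocol*

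**What the plan says.** Protocol Appendix 2 models the logit of the response rate as linear in log(dose/75), with independent normal priors on intercept and slope. The prior starts from four rates: "It is assumed that the response rate at dose of 75mg, 225mg, 675mg, and 1500mg to be 0.2, 0.4, 0.55 and 0.7 respectively". Regressing their logits on log dose gives means of -1.33 and 0.72. The SDs, 0.45 and 0.2, are set so that the 97.5% quantile at the lowest dose is near 0.4 and the 2.5% quantile at the highest dose is near 0.35. The appendix then concludes, from the width of the 95% band before any data, that the prior has "weak impact on the posterior estimation of response rate when data are observed".

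Appendix 2 and Protocol 8.5 allow the model to be used as early as the opening of cohort 3. Appendix 2 advises that prediction is more reliable later, for example before cohort 4. Titration results may be added: the proposal is to "combine the subjects at two adjacent cohorts to estimate the response rate at the higher dose" shared by those cohorts. Under Protocol 3.1.3 the model may be used to "predict a dose satisfying certain efficacy criteria, which might be different from the standard", so the target response rate is left open. Under both 3.1.3 and Appendix 2 the selected dose may not exceed the planned one.

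The simulation settings are "Rate: 0.2, 0.4, 0.55, 0.7" and "Conditional response rate for non-responder after titration: 0.25, 0.25, 0.33", with a target of 0.7. The reported result is that "Bayesian modeling provides less variant and seemingly closer-to-true-value predictions compared to the usual logistic regression".

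**The concern.** How far a prior moves an estimate depends on its information relative to the data, not on how wide its interval looks. With 10 subjects per dose, and none yet at the doses to be predicted, a wide interval can still outweigh the data. A reader who accepts the sentence would treat a cohort 3 prediction as driven by the data when about half of it, or more, is the design assumption.

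The simulation does not fill the gap. A prior centred on the truth will look both less variable and closer to the truth. That says nothing about performance when the assumed rates are wrong, which is when an adaptive dose choice is most needed.

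**Working it through.** **Reproducing the stated prior.** With x = ln(dose/75) = 0, 1.099, 2.197, 2.996, least squares on logit(0.2, 0.4, 0.55, 0.7) gives (-1.325, 0.724). The prior SD of the logit is √(0.45² + 0.2²x²) = 0.450, 0.501, 0.629, 0.749. The 97.5% quantile at 75 mg is expit(-1.33 + 1.96×0.45) = 0.390. The 2.5% quantile at 1500 mg is expit(-1.33 + 0.72×2.996 - 1.96×0.749) = 0.345. All agree with Appendix 2, so the prior itself contains no arithmetic error.

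**Effective sample size.** On the response scale, ESS = m(1-m)/variance - 1. Prior means are 0.218, 0.375, 0.557, 0.676 and SDs 0.075, 0.111, 0.142, 0.149. This gives about 29, 18, 11 and 9 subjects.

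**Share of prior variance removed by the data.** This is 1 - E[posterior variance]/prior variance of the response rate, averaged over the prior predictive distribution (grid posteriors, every outcome enumerated).

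| Data | 75 | 225 | 675 | 1500 mg |
|---|---|---|---|---|
| Cohorts 1-2, start dose (10+10) | 43% | 45% | 36% | 30% |
| Same, with cohort 1 titration counted as n=20 at 225 mg | 52% | 58% | 49% | 41% |
| Cohorts 1-3, start dose (10+10+10) | 49% | 62% | 60% | 55% |

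The second row treats the 20 as independent of the 75 mg results. That overstates the data, because titrated subjects also count at 75 mg.

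**Hand check on the logit scale, 10+10.** The prior precisions are 1/0.45² = 4.938 and 1/0.2² = 25. The data weights n·p(1-p) are 10×0.2×0.8 = 1.6 and 10×0.4×0.6 = 2.4. The posterior precision matrix has diagonal 4.938 + 4.0 = 8.938 and 25 + 2.4×1.099² = 27.897, off-diagonal 2.4×1.099 = 2.637, and determinant 242.4. The posterior variance at 75 mg is 27.897/242.4 = 0.115, which is 0.57 of the prior 0.2025. The other doses give 0.54, 0.62 and 0.68. This is a different measure with the same conclusion. With only 5 subjects in cohort 2 the shares are 0.64, 0.65, 0.72 and 0.77.

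**Worked example.** With 5/10 and 7/10 responders the posterior means are 0.34 and 0.54. These lie (0.339-0.218)/(0.5-0.218) = 43% and (0.544-0.375)/(0.7-0.375) = 52% of the way from prior to data.

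**The simulation.** Its rates are those that built the prior. Its titration rates are the same curve re-expressed: 0.2 + 0.8×0.25 = 0.40; 0.4 + 0.6×0.25 = 0.55; 0.55 + 0.45×0.33 = 0.70. The prior mean alone places a 0.7 rate at 75·exp((0.847+1.33)/0.72) = 1543 mg, beside the simulated truth of 1500 mg.

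**Effect on an early prediction if true rates are higher.** Assumption: the prior curve shifted by +1 logit (0.42, 0.61, 0.78, 0.86), with 10+10 start-dose results. The comparator is an illustrative weaker positive-slope prior: intercept SD 1.0 and log-normal slope with median 0.72 and log-SD 0.5, worth 5.8, 4.1, 3.1 and 2.8 subjects. The model dose is where the posterior mean response reaches the target t. The true target dose is 75·exp((logit t + 0.33)/0.72). RMSE is on the log dose after capping at 675 mg. Each cell gives stated v weaker prior.

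| Target | True dose | Median prediction | Below 675 mg cap | RMSE after cap |
|---|---|---|---|---|
| 70% | 385 mg | 698 v 428 mg | 39% v 75% | 0.49 v 0.46 |
| 60% | 208 mg | 396 v 233 mg | 92% v 96% | 0.72 v 0.55 |
| 55% | 157 mg | 296 v 186 mg | 98% v 98% | 0.74 v 0.56 |

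Outcomes are discrete, so medians are coarse. At 70% under the stated prior, the 45th-55th percentile range is 684-768 mg.

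**If the assumed rates hold** (70% target, start-dose data), RMSE before the cap is 0.49 v 0.88, and the prediction falls below the cap in 1% v 17% of trials. All doses here are model illustrations, not recommendations.

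**The case against.** The strongest reply is that an informative prior is needed here. Under the assumed rates about 33% of 10+10 datasets show a non-positive slope or no responder at 75 mg, so ordinary logistic regression gives no usable dose. The stated prior is also clearly more accurate when its rates are right. That stands, and it is a reason to keep the prior. It is not a reason to call the prior's influence weak.

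The prior is also fully stated, so any reader could work out its weight, and no decision rule rests on the sentence. At the advised later use the data outweigh the prior at every dose but 75 mg. These points limit the consequence and stand as such.

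The weaker prior is one choice among many and relaxes two of Appendix 2's guidelines: its 97.5% quantile at 75 mg is 0.65, and its 2.5% quantile at 1500 mg is 0.17. The +1 logit scenario lies 1/0.45 = 2.2 prior SDs out on the intercept. So the dose contrasts show direction and rough size only. The effective sample sizes and variance shares depend on neither choice.

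A reader might infer that no off-centre simulation was ever done. The documents do not support that: Figures 1 and 2 are not shown, Appendix 2 defers detail to the SAP, and parts of the SAP are redacted.

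**Conclusion.** The inference of weak influence is not supported at the earliest permitted use, where the prior carries roughly half the weight or more. Before cohort 4 it keeps about 51%, 38%, 40% and 45% of its variance at the four doses, so it no longer dominates except, narrowly, at 75 mg. The visible simulation cannot show performance when the assumed rates are wrong.

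If rates are higher than assumed, early predictions are pulled upward at every target examined. The form of the effect differs by target. At 70% the prior mainly changes how often the prediction falls below the cohort C cap, while error after the cap is similar. At 55-60% cap-crossing barely changes, but the predicted dose is clearly less accurate. A reader who looked only at cap-crossing would wrongly place the harm at 70% alone.

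Two stronger readings should be resisted. One is that the prior is miscalculated or should be replaced: its arithmetic reproduces, and it is the more accurate prior if its rates hold. The other is that the prior will determine the trial's doses: use is optional, other models (including exposure-based ones) are allowed, waiting is advised, and the dose is capped at plan.

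The prior weights rest on the Appendix 2 model and full cohorts of 10. The dose contrasts rest also on the +1 logit scenario and the illustrative comparator. The point merits correction but does not threaten the trial.

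**What to change.** 1. Replace the sentence on the prior's influence with its effective sample size at each dose and its share of the posterior at both the cohort C and cohort D decision points.
2. Whenever the model informs a cohort dose, report the prediction under the stated prior as primary and, as a sensitivity analysis, under a weaker positive-slope prior fixed in advance. The prior used above is one example.
3. Unless the redacted SAP text already has them, add simulation scenarios away from the prior centre (flat, low, high, plateau), with and without titration data, for the target rate actually to be used. Judge them by error in the selected, capped dose and not only by how often it falls below the cap.

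The cost is a few sentences and a short simulation. The sensitivity prediction will be more variable when the assumed rates are right: at a 70% target it falls below the cohort C cap in 17% of trials against 1% with start-dose data, and 13% against 3% with titration data. It should therefore sit beside the stated prior and not replace it.
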